## **5.9 Engagement**

Asking people to actively symptom monitor for a 12-month period might be challenging. Following a systematic review of what improves retention in clinical studies (Edwards, et al., 2009), and following consultation with our advisory groups, a variety of strategies to mitigate user disengagement will be implemented, which may include:

- providing participants with a mobile phone and a wearable device plus the cost of data plan at £10 per month for up to 12 months;
- regular phone calls to troubleshoot technical difficulties and check-in; workshops, newsletters, engagement events to update participants on project progress and to create a sense of inclusion/identity with CONNECT;
- thank you cards following assessments;
- a regular non-personalised email (shown to lead to improved engagement);
- a semi-automatic email/text to allow people to directly report issues; resource/toolkit section from the Actissist app ([name], et al., 2018), comprising self-help resources, recovery stories, mindfulness/relaxation guides, links to helpful website/blogs/forums;
- rewards/badges earned when a significant percentage of data points are completed each week; motivation reminders sent by push notifications to prompt participants to complete questions.

Participants will be able to view their data in a relevant and accessible format (with support from a researcher) on the participant-facing dashboard at study end.

We will give participant's the option to pause the prompt schedule if they would like a break from receiving regular notifications.

No constraints are placed on referring services on their practice. Similarly, participants in receipt of services will be encouraged to continue to access their clinical service according to their local care co-ordinator, psychiatrist and other care planning arrangements. There are no requirements from the CONNECT study for participating teams to change or modify their existing practice in response to study procedures.

## **5.10 Withdrawal criteria**

Participants wishing to withdraw from the study will be free to do so at any time. There may be several reasons for withdrawal from the study:

- i. participant choosing to no longer participate: participants will be informed both in writing and verbally that participation is voluntary, that non-participation will not influence their medical care, and that they are free to withdraw from the study at any point without providing reasons;
- ii. the research team may withdraw the participant in the event of serious adverse event (SAE), protocol violation, administrative or other reasons;
- iii. the participant loses capacity for continued participation.

In the case of participant self-withdrawal, all attempts will be made to follow-up with the participant to establish cause of withdrawal, and to collect qualitative data regarding experience of participation.

Psychosis relapse itself is not cause for automatic withdrawal; unless they choose to stop, participants who are identified as experiencing a relapse will continue to participate until study end-point. All data, including those from withdrawn participants, will be retained and included in the final analysis. No further data will be collected or any other research procedures carried out in relation to a withdrawn participant.

Withdrawing participants will be able to request deletion of data from the dataset if they wish. However, participants will be unable to withdraw their data after the destruction of the pseudo key. After this time, data will be anonymous and it will be impossible to identify.

There can be a time lag on accessing clinical notes. In the event a participant withdraws from the study and does not request deletion of data from the dataset, clinical notes may be accessed after the point of withdrawal, but only for records up to the date of withdrawal. In the event the participant requests the deletion of all study data, no further data will be extracted.

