Secondary	To derive and validate an adaptive sampling regimen for maximising engagement and information obtained from digital remote monitoring (DRM)	Disengagement with DRM devices

	Acceptability of a wearable device	Assessment of data collected; satisfaction questionnaire
	Acceptability of DRM and study procedures	Participants report procedures are acceptable via qualitative interviews and satisfaction questionnaire
Eligibility Criteria	
Inclusion criteria:
 
 
(i) Adults (16 years and over);
 
(ii) within the past two years have had at least one acute episode of psychosis (including relapse and first episode) leading to an unscheduled episode of acute care, including inpatient admission or acute home treatment/crisis intervention;
 
(iii) received a clinical diagnosis of, or confirmed by the treating clinician to meet the criteria of, schizophrenia spectrum disorder (ICD10 F20-29);
 
(iv) current presentation does not include severe acute symptoms;
 
(v) in accordance with the Mental Capacity Act, mental capacity will be assumed. If there is any doubt, then a capacity assessment will be carried out by a clinician from the study team or the responsible clinician.
 
 
Exclusion criteria: Experienced a recent relapse within the previous 12 weeks as confirmed by the treating clinician; non-English speaking.
	
Statistical Methodology and Analysis	
Extraction of sensor features; estimate association between these features and clinical status using mixed-effects models and unsupervised machine learning.
 
Regression modelling and other supervised machine learning approaches to develop risk prediction algorithm.
 
Information and decision theoretic methods to build adaptive sampling algorithm.
 
Qualitative methods (e.g. Framework analysis) to measure acceptability.
	

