#### **5.4 Follow-up assessments (approx. 90 minutes)**

In a previous version of the protocol, participants consented into the study up to mid-January 2025 followed a 3, 6, 9, 12 month assessment schedule. Following an ethical amendment, clinical measures and review of medical records will take place at baseline and every 4 months thereafter (i.e. repeated at 4, 8, and 12 months)\*. See section 5.8 for a description of clinical measures. Regular assessments are undertaken to label and validate behavioural data collected from the passive and contextual data collected via the smartphone and wearable device.

Research workers will be trained in the use of all the instruments and scales, to achieve a satisfactory level of inter-rater reliability. Regular training sessions including the use of video and role play will be conducted to maintain reliability and prevent rater drift. Participants will be offered choices regarding length of assessments, including the option of breaks and multiple occasions.

At the final follow-up meeting (12 months), participants will be given the opportunity to debrief about the study. We will also remind people that they can keep their wearable device and phone (if received a study phone) and that we will no longer pay for mobile phone data. We will also give participants the opportunity to view and discuss their data. We expect this final 12-month visit to take approx. 90 - 120 minutes to complete (for those who wish to discuss their data).

Assessments will be done in person if possible, or remotely if more convenient (or restrictions dictate so). Self-report assessments can be completed online via a link.

In the event a participant withdraws from the study before 12 months, permission will be sought to conduct a qualitative interview to understand their reasons (Appendix E). Participants will also be able to view their data and debrief about the study, but only if they wish.

*\* Those participants who have previously consented into the study will be able to continue with quarterly assessments (i.e. repeated at 3, 6, 9 and 12 months), or they will be offered the option to re-consent and follow the updated assessment schedule.*

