#### **5.5 Qualitative exit interview (approx. 60 minutes)**

An in-depth qualitative exit interview will be carried out with a purposively selected group of participants at the point of drop-out (number not specified) or at the end of the study with approx. 10 participants per recruitment site (or until data saturation is reached). Participants will be informed about and asked to consent to the qualitative interview when information is provided and consent taken for the cohort study. Participants will be selected according to a sampling framework to capture

varied demographics and levels of engagement with the DRM platform. Participants who consent to take part will be asked to complete this qualitative interview as part of an in-person or remote meeting with a research worker.

Participants will be asked questions that seek to find out, for example:

- i. how they found the DRM platform;
- ii. what level of support might be needed to facilitate engagement with the platform;
- iii. overall impressions of the platform (e.g. what participants liked and/or did not like about the platform in terms of content and usability);
- iv. how the platform helped and/or did not help;
- v. what changes we should make;
- vi. barriers and facilitators to use, engagement, and longer-term use (see Appendix G, Topic Guide).

Data obtained throughout the course of qualitative work will be used, if necessary, to make iterative developments to the platform software, to optimise usability of the system.

The interviews will be audio-recorded for transcription and analytic purposes using devices enabling password protection at the point of recording. Meetings will take approximately 60 minutes, depending on the extent to which the participant requires breaks or further support / guidance and to include a full debrief.

In-person meetings will only take place after satisfactory risk assessments (COVID-19 and other risks) and appropriate mitigation procedures have been put in place (e.g. ensuring meetings take place in sufficiently ventilated rooms / locations). In-person meetings will take place at locations that are mutually convenient for research workers and participants (these can include the participant's home, NHS premises, University premises).

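### Section 5.10 both promises and forbids collecting the experience of withdrawn participants, and neither schedule offers the satisfaction scales at withdrawal

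*Protocol*

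**What the plan says.** Section 5.10 gives two instructions for a participant who has withdrawn. For self-withdrawal, "all attempts will be made to follow-up with the participant to establish cause of withdrawal, and to collect qualitative data regarding experience of participation". For any withdrawn participant, "No further data will be collected or any other research procedures carried out in relation to a withdrawn participant". It adds one exception, for records: "clinical notes may be accessed after the point of withdrawal, but only for records up to the date of withdrawal". Data already given are kept: "All data, including those from withdrawn participants, will be retained and included in the final analysis", subject to a participant's right to ask for deletion.

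Two other sections plan contact at the same moment. Section 5.4 says that, on withdrawal before 12 months, "permission will be sought to conduct a qualitative interview to understand their reasons". Section 5.5 plans exit interviews at drop-out with a purposive sample, leaves their number open, and asks for interview consent when consent to the cohort is taken.

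The outcomes concerned are the acceptability of the wearable and of remote monitoring and study procedures, both secondary outcomes in section 3.5. The Study Summary measures the first by the data collected plus a satisfaction questionnaire. It gives the second as: "Participants report procedures are acceptable via qualitative interviews and satisfaction questionnaire". Appendices 1 and 2 place technology satisfaction and the PSSUQ at scheduled visits only.

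**The concern.** An interview about the experience of taking part is both data and a research procedure, so the ban, read literally, rules out what the preceding paragraph of 5.10 and sections 5.4 and 5.5 call for. Staff at six sites could not satisfy both. If the ban is followed, the experience of those who leave drops out of the interview part of a named secondary outcome.

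The questionnaire part has a related gap that does not depend on how the ban is read. Dissatisfaction is a plausible reason for leaving, and nothing in the schedules offers a rating at the point of leaving. The protocol itself treats attrition as a subject of study: section 6.2.2 wants to know what predicts it, and section 6.4.3 models time to drop-out. Reasons for leaving, recorded in a comparable way, would serve that work too.

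**Working it through.** The protocol states no figure on this point, so the check sets the texts side by side.

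**1. What may happen after withdrawal**

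| Place | Who | Rule |
|---|---|---|
| 5.10, self-withdrawal sentence | Self-withdrawn | Every attempt at follow-up, for cause and qualitative experience |
| 5.10, ban | Any withdrawn participant | No further data, no procedures |
| 5.10, exception | Withdrawn, no deletion requested | Clinical notes, up to the withdrawal date |
| 5.4 | Withdrawn before 12 months | Interview, if permission is given |
| 5.5 | Purposive sample at drop-out | Exit interview, for those who consent |
| 5.7 | Loss of capacity | Nearly the same ban, limited to this case |

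The first, fourth and fifth rows point the same way: some contact takes place. The second row contradicts all three. The third row shows that an exception was drafted in 5.10, and it does not mention the interview. The last row shows similar wording in a setting where no interview is planned; in 5.10 it covers every type of withdrawal.

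The rows that allow contact also differ in strength. The first calls for every attempt, while 5.4 asks for permission. Section 5.10 also tells participants that they need give no reason for leaving.

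**2. When a rating can exist**

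- Quarterly schedule (Appendix 1): technology satisfaction and PSSUQ at months 3, 6 and 12.
- Four-monthly schedule (Appendix 2): two marks, apparently months 4 and 12. The table is broken in the text available, so the months are a reading and not a certainty.
- Neither schedule has a withdrawal column. Both mark the exit interview only at 12 months, although 5.5 also places it at drop-out.

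| Time of leaving | Quarterly | Four-monthly (as read) |
|---|---|---|
| Before first follow-up | None | None |
| After month 3, before month 6 | Month 3 | None before month 4, month 4 after it |
| After month 6, before month 12 | Months 3 and 6 | Month 4 |

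No leaver has a rating taken at exit.

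**3. Can the effect be sized?**

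That would need the number who formally withdraw, when they do so, and how their ratings differ from those of people who stay. The protocol gives none of these. Section 6.2.2 cites retention from earlier trials (85% at 12 months in one, 84% at 6 months in another), but non-retention includes people lost to contact and is not a count of withdrawals. No magnitude is therefore offered.

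**The case against.** The strongest reply is that the contradiction is a missing clause. Sections 5.4 and 5.5 and the self-withdrawal sentence of 5.10 together describe a consented exit interview. A sensible reader lets the specific text govern the general: routine data stop and the interview proceeds. The protocol also provides standardised training (7.4) and weekly supervision of research workers (8.1), and nothing in it reports that sites act differently. This is fair as a guess at intent, and divergent practice is a risk rather than an observed fact. The ban still has no such exception, while a different one is written beside it, so the text needs correcting.

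A second reply is that section 6.3 already handles wholly missing questionnaires: they are recorded and multiply imputed as missing at random, with sensitivity analyses if they may be informatively missing. That stands as an analysis provision. It is a weak substitute for a rating when dissatisfaction may itself drive leaving. Denominators and bounds in reporting can be left to the SAP and are not part of this point.

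A third reply is that a reader might infer that the acceptability outcomes rest mainly on people who stayed. The documents do not support that. Section 5.5 plans drop-out interviews and samples across levels of engagement. Wearable acceptability also uses the device data collected, section 5.8.1 treats loss of a data stream as an acceptability metric, ratings given before withdrawal are retained, and nothing makes the month-12 rating the only measure. The interview part would rest on stayers only if the ban overrode 5.4 and 5.5.

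Finally, extra questionnaires burden people who are leaving. That is true, which is why the offer must be voluntary and made once.

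**Conclusion.** Two things hold. Section 5.10 contradicts itself, and its ban contradicts 5.4 and 5.5, so the passages must be reconciled. The satisfaction questionnaire and PSSUQ have no administration at withdrawal. People who leave before the first follow-up therefore contribute no rating and later leavers only earlier ones, which opens the questionnaire part of the two acceptability outcomes to selection.

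The size of that selection is unknown. It would be tempting to apply the cited retention rates to the planned 1100 and read the shortfall as withdrawals whose views are missing, but that step is not supported, for the reasons in the check above. The direction, with leavers less satisfied than stayers, is plausible but assumed.

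The effect is confined to secondary acceptability outcomes and to the comparability of reasons for leaving. The primary relapse model is untouched. The change is worth making because it is cheap and because analysis cannot recover ratings that were never requested.

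**What to change.** Reconcile 5.10 with 5.4 and 5.5 in one consent-based rule. After self-withdrawal, the ban on further data and procedures has one stated exception besides the clinical notes: a single voluntary exit contact. If the participant agrees, it records a reason category, the technology satisfaction questionnaire and the PSSUQ, and offers the optional interview. If the participant declines, no further contact is made. Replace the commitment to make every attempt with this rule, and leave the loss-of-capacity rule in 5.7 as it is.

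Add an early-withdrawal column with these items to the assessment schedules, for withdrawals from the amendment onwards.

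The cost is a small amendment, a change to the information sheet, and a slight burden on those who agree. Both scales are already in use, and 5.4 already allows a contact at this point. The change will not capture people who have already left, who decline, or who are lost to contact, so some selection will remain.

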## **5.11 End of study**

The end of the study is defined as the last participant completing their debrief interview, or at the completion of the last qualitative interview, whichever comes last.

At the end of the research study, we will notify the review bodies that the study has ended and provide final reports, confirm arrangements for future use of research data, and publish the results of the research.

## **6 Statistics and Data Analysis**

Statistical aspects of the study have been developed by the statisticians within the research team. A pre-specified analysis plan will be developed.

### **6.1 Sample size calculation**

With a relapse rate of between 25% (commonly reported in literature) and 40% (found in our NIHR-funded EMPOWER study) in a 12-month period, 1100 participants (800 for training, 300 for validation) are required. This is based on sample size criteria for prediction models of binary outcomes (Riley, et al., 2018), allowing for the (correlated) repeated measures at the individual level. Specifically, pilot analyses on the ClinTouch and EMPOWER datasets for this proposal, found that the within-person correlation of the most asked questions in these datasets were 0.52 and 0.51, respectively. If we assume our risk prediction algorithm will explain 15% of the maximum variation, then our sample size will be sufficient to develop an algorithm with between 5-7 predictor variables (depending on the exact relapse rate). We therefore aim to recruit a total of 1100 relapse-prone individuals across six UK sites.

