### **6.2.2 Attrition**

We acknowledge that there might be some level of loss-to-follow-up. We will monitor attrition closely. In our previous digital psychosis trials, dropout rates have been low (e.g. retention rate in EMPOWER at 12-months of 85%; and 84% in Actissist 2.0 at 6-month follow-up). We will use evidence-based strategies to maximise retention and minimise loss to follow-up (see section 5.9, Engagement). In the case of large attrition, we can still build a risk prediction algorithm; however, we may need to build an algorithm based on fewer predictors (e.g. 4 - 6 instead of 5 - 7). Nonetheless, attrition is of direct interest for the adaptive sampling algorithm part of the study as we would like to know what predicts attrition and then incorporate this knowledge in an adaptive sampling algorithm to mitigate attrition in future DRM studies. Our primary outcome (relapse) should be available for almost all participants as we will be able to access medical records, which will document this outcome.

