We will develop the risk prediction algorithm using Group 1 ( $n = 800$ ), which will then be validated and refined as needed in Group 2 ( $n = 300$ ). Under the assumption that data will be missing at random, multiple imputation will be applied for covariates, any covariates with over 60% missingness will be excluded in the interests of clinical utility (see Section 6.3). The primary outcome will be the binary indication of relapse in either, for example, 7 days (model 1) or 28 days (model 2) from time-of-prediction. For an individual participant, such outcomes will be defined in a 'rolling manner', where we define outcomes at the end of each week (model 1) or each month (model 2). To achieve the best performing model, we will consider a range of analytical models, including (but not limited to): logistic regression, artificial neural networks, support vector machines, random forests, hidden Markov models, and Bayesian approaches. For example, the hidden Markov models will use certain features of an individual's inputs (ASM and PSM) and use the data to calculate for each individual a risk of being in one of a small number of mutually exclusive 'states' which correspond to, for example, remission, deteriorating, relapse. The data will also allow a day-to-day calculation of instability ('entropy') – the likelihood of remaining in that state (Figure 5). Individuals can 'switch' between states. We will include interactions between predictors to allow certain subgroups of individuals to have slightly different 'versions' of the algorithm; that is, tailor the model to subgroups across the heterogeneous target population.

[figure not shown]

Figure 5. Graphical representation of algorithm functionality

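### The stated capacity of 5–7 predictors fits the 28-day model only; the same calculation gives about 2 for the 7-day model

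*Protocol*

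**What the plan says.** Section 6.1 of the protocol starts from the 12-month relapse proportion: "With a relapse rate of between 25% (commonly reported in literature) and 40% (found in our NIHR-funded EMPOWER study) in a 12-month period". It then says that "1100 participants (800 for training, 300 for validation) are required", on the basis of "sample size criteria for prediction models of binary outcomes", "allowing for the (correlated) repeated measures at the individual level". The within-person correlations are 0.52 and 0.51, taken from app questions in two earlier datasets. The model is assumed to explain 15% of the maximum variation. The result is one figure: "our sample size will be sufficient to develop an algorithm with between 5-7 predictor variables", said to depend on the exact relapse rate and on nothing else.

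Section 6.4.2 describes two models: "The primary outcome will be the binary indication of relapse in either, for example, 7 days (model 1) or 28 days (model 2". Outcomes are defined weekly for model 1 and monthly for model 2. Sections 3.1 and 3.4 name both horizons as well. Section 6.2.2 adds that if attrition is heavy "we may need to build an algorithm based on fewer predictors (e.g. 4 - 6 instead of 5 - 7". No capacity is given for either horizon by name.

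**The concern.** The number of parameters that a development sample supports depends strongly on the event fraction per row. A weekly window carries roughly a quarter of the risk of a monthly one. Adding more rows per person does not compensate when the assumed within-person correlation is about 0.5. One range therefore cannot describe both models, and 6.1 does not say which one it describes.

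Two decisions rest on the figure. Section 6.4.2 plans a list of candidate predictors with interactions, and a team that reads 5–7 as covering both models would size the 7-day list too generously. The same section allows data collection to stop once performance is adequate and the minimum sample size criteria are met. If the criteria are known for one model only, that condition is ambiguous for the other.

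**Working it through.** **Inputs from the protocol.** Development sample N = 800; annual relapse a = 0.25 to 0.40; ρ = 0.51 to 0.52; explained fraction 15% of the maximum (all section 6.1). Weekly or monthly windows (section 6.4.2) over 12 months of follow-up (section 5.6.1).

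**Assumptions, because the protocol states none of them.** Shrinkage target S = 0.90; design effect 1+(m−1)ρ; constant risk across windows.

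**Formulas.**
- Effective rows: n_eff = N·m / (1+(m−1)ρ)
- Risk per window: φ = 1 − (1−a)^(1/m)
- Maximum R²: 1 − exp(2[φ ln φ + (1−φ) ln(1−φ)]); R² = 0.15 × maximum
- Parameters supported: P = n_eff·(S−1)·ln(1 − R²/S)

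**Step 1: reproduce the printed figure (monthly, m = 12).** With ρ = 0.52, n_eff = 800×12/(1+11×0.52) = 1429; with ρ = 0.51 it is 1452. φ = 0.0237 to 0.0417, and maximum R² = 0.201 to 0.293.
- At a = 0.25: R² = 0.0301, so P = 1429 × 0.1 × 0.0340 = 4.9.
- At a = 0.40: R² = 0.0439, so P = 1429 × 0.1 × 0.0500 = 7.15, or 7.3 with ρ = 0.51.

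The range 4.9–7.3 matches the printed 5–7. Thirteen 28-day windows give 4.6–6.9, which also rounds to 5–7. One 12-month row per person gives 9.6–10.5, which does not match. Reducing N to 680 (0.85 × 800) gives 4.1–6.2 with monthly windows, which matches the 4–6 in section 6.2.2. One set of assumptions thus reproduces both printed ranges.

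**Step 2: same calculation for the 7-day model (m = 52).** With ρ = 0.52, n_eff = 800×52/(1+51×0.52) = 1512; with ρ = 0.51 it is 1540. φ = 0.0055 to 0.0098, and maximum R² = 0.066 to 0.104.
- At a = 0.25: R² = 0.0099, so P = 1512 × 0.1 × 0.0111 = 1.7.
- At a = 0.40: R² = 0.0156, so P = 1512 × 0.1 × 0.0175 = 2.65, or 2.7 with ρ = 0.51.

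**Step 3: sensitivity to the assumed target (N = 800).**

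| S | Monthly windows | Weekly windows |
|---|---|---|
| 0.85 | 7.7–11.6 | 2.7–4.3 |
| 0.90 | 4.9–7.3 | 1.7–2.7 |
| 0.95 | 2.3–3.4 | 0.8–1.3 |

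Of these targets only 0.90 reproduces the printed range, and at none does the weekly model reach 5. If φ is taken as a/52 instead, the weekly result at S = 0.90 and ρ = 0.52 is 1.5–2.2.

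**Step 4: sensitivity to the correlation.** With ρ = 0.2, weekly n_eff = 41,600/11.2 = 3714, so P = 1.67×3714/1512 = 4.1 up to 2.65×3714/1512 = 6.5. Monthly n_eff = 9600/3.2 = 3000, so P = 4.86×3000/1429 = 10.2 up to 7.15×3000/1429 = 15.0. Both figures move, and the gap between the horizons remains.

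**Step 5: size of the gap.** At S = 0.90 and ρ = 0.52, five parameters at 7 days would need 800×5/1.67, about 2,400 development participants at 25% relapse, or 800×5/2.65, about 1,500 at 40%. The plan has 800.

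**The case against.** **The method is inferred.** The protocol gives no shrinkage target, design-effect form or window count, so the match to 5–7 was found by trying combinations. That is fair, and the conclusion must be labelled accordingly. The same assumptions also return the 4–6 of section 6.2.2, which makes the reading credible but does not make it the stated method.

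**The correlation may not apply to relapse.** It comes from app questions, and carrying it over 52 rows of an outcome with a weekly risk below 1% drives the low result. Repeat relapses, possible because participants continue after a relapse (section 5.10), would also raise the event rate. Both points stand. They limit what can be claimed about the 7-day model, but they do not make one figure valid for both horizons.

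**Penalisation is planned.** Section 6.4.2 uses penalised regression against overfitting. This lessens the practical harm but does not correct the stated capacity.

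**A reader might go further on attrition.** Because N = 680 yields 4–6, and section 6.2.2 reports a "retention rate in EMPOWER at 12-months of 85" per cent, it is tempting to call 4–6 the expected case and to print 1–2 for the 7-day model. The documents do not support this. Section 5.10 keeps withdrawn participants' data unless they ask for deletion, and section 6.2.2 expects relapse to be available from records for almost everyone. With ρ near 0.5, a person's later rows add little. If 15% leave at evenly spread times, effective n falls by only about 1–3%, which leaves 4.7–7.1 for monthly windows and 1.7–2.7 for weekly ones. Multiplying by 0.85 treats those who leave as contributing nothing.

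**A reader might also infer that the primary conclusion can drift to the better-looking horizon.** The wording in 6.4.2 is loose, but sections 3.1 and 3.4 name both horizons, and 6.4.2 selects a method for each model. Demoting the 7-day outcome would change the study's stated aim and does not follow from this point.

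**Conclusion.** The point holds. Section 6.1 states a single capacity for two primary models. Under the one simple set of assumptions that reproduces it, the figure belongs to the 28-day model, and the 7-day model gets about 2 (1.7–2.7), staying below 5 for shrinkage targets from 0.85 to 0.95. The printed arithmetic is not wrong; its scope is overstated.

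The result rests on an assumed target of 0.90, the design effect 1+(m−1)ρ with the protocol's 0.51–0.52, and constant risk per window. It means that the protocol's calculation, as reconstructed, shows no support for 5–7 predictors at 7 days. It does not mean that a 7-day model is infeasible: a well-justified lower correlation could bring it to 4.1–6.5 (at 0.2), with the 28-day figure rising as well.

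**What to change.** In section 6.1:

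1. State that 5–7 applies to the 28-day model.
2. Give the 7-day capacity separately, about 2 on present inputs.
3. Report the shrinkage target, the number of windows per person and the design effect used for each.
4. Either limit the 7-day model's candidate parameters to its own capacity, or justify a different correlation for the relapse outcome and recompute both figures.

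Section 6.2.2 needs no change on this account, and both horizons can stay primary. The cost is one recalculation and some text, with no change to recruitment or data collection. The downside is a less favourable stated figure for the 7-day model.
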